#### 6.8 Appendix 8: Derivation of Overall UDS Result for Opioids Use

efficacy endpoints analyses in this SAP. A urine dipstick is performed onsite at Screening, Induction Day 1, and Week 6. UDS samples for all other scheduled visits are tested centrally. In the case that a central UDS sample was not submitted for a scheduled visit, the onsite dipstick UDS, if available for that visit, will be used.

#### 6.8.1 Centrally Tested UDS

Centrally tested UDS provides individual results (negative or positive) for each of the different opioid drugs being tested. To derive the centrally tested overall opioids UDS result, the UDS fentanyl test result will be derived first. Then, results from 3 tests (opiates, fentanyl, methadone) will be used.

The centrally tested UDS fentanyl test result will be based on "Fentanyl" and "Norfentanyl" test results. The algorithm to determine the central UDS fentanyl result is as follows:

- "Fentanyl Positive" if either of the 2 test results is positive.
- "Fentanyl Negative" if both test results are negative; or if 1 is negative and the other is missing.
- "Fentanyl Missing" if both test results are missing.

The algorithm to determine the centrally tested overall UDS opioid result for each visit uses the 3 individual results (fentanyl, opiates, methadone) as follows:

- "Opioid Positive" if at least 1 individual test result is positive.
- "Opioid Negative" if all 3 individual test results are negative.
- "Opioid Missing" for other scenarios, eg, if all 3 individual test results are missing, or if
  one test result is missing and the other 2 individual test results are either negative or
  missing.

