8.3.1 Urine Drug Screening

Dipstick and centrally tested UDS will include substances listed in Table 1. A urine dipstick will be performed on-site at Screening, first TM buprenorphine induction day/Day 1 and Week 6. All other UDS will be tested centrally. Additional unscheduled

UDS (dipstick) may be performed as determined by the Investigator or a medically qualified sub-Investigator as per standard-of-care and/or if abuse is suspected.

Additional information related to the collection and handling of urine specimens is located in the laboratory manual.

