#### 6.8.2 On-site dipstick UDS

Individual test results for opioids and morphine from the on-site dipstick UDS will be combined into 1 result for opioids/morphine. The algorithm to determine the combined result is as follows:

- "Opioids/morphine Positive" if at least 1 of the individual test results is positive.
- "Opioids/morphine Negative" if both test results are negative; or if 1 is negative and another is missing.
- "Opioids/morphine Missing" if both test results are missing.

The algorithm to determine the on-site dipstick overall UDS opioid result uses 4 test results (1 combined test result for opioids/morphine, and 3 individual test results for oxycodone, methadone, fentanyl) as follows:

- "Opioid Positive" if at least 1 test result is positive.
- "Opioid Negative" if all 4 test results are negative.
- "Opioid Missing" for other scenarios, eg, if all 4 test results are missing; if opioids/morphine is missing and the other 3 test results are negative or missing; if the fentanyl test result is missing and at least one of the other 3 test results is negative.

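### The central overall opioid UDS rule in SAP 6.8.1 leaves out oxycodone and the dipstick rule in 6.8.2 counts it; unless central opiates covers oxycodone, one by-visit summary mixes two definitions

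*SAP*

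**What the plan says.** SAP 6.8.1 sets the central rule. It first notes that "Centrally tested UDS provides individual results (negative or positive) for each of the different opioid drugs being tested". It merges fentanyl and norfentanyl into one fentanyl result, and then "results from 3 tests (opiates, fentanyl, methadone) will be used". Any positive makes the visit opioid-positive; three negatives make it opioid-negative. Oxycodone does not appear.

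SAP 6.8.2 sets the dipstick rule. Its inputs are "1 combined test result for opioids/morphine, and 3 individual test results for oxycodone, methadone, fentanyl". Any positive makes the visit opioid-positive, and all four must be negative for an opioid-negative visit.

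Protocol 8.3.1 says "Dipstick and centrally tested UDS will include substances listed in Table 1". In that table Oxycodone is an entry of its own, beside Opioids, Fentanyl, Morphine and Methadone.

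SAP 6.8 assigns the methods to visits: "A urine dipstick is performed onsite at Screening, Induction Day 1, and Week 6", with other scheduled visits tested centrally. It also gives a fallback: where a scheduled visit has no central sample, an available dipstick result takes its place.

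SAP 5.7.3 reports the overall opioid result by visit in a single summary, and 5.7.6 repeats the UDS results for the fentanyl-positive and fentanyl-negative subpopulations. SAP 6.2, which lists changes from the protocol's analyses, does not mention oxycodone.

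**The concern.** A series reported by visit should mean the same thing at every visit. Here the written rule changes with the test method, and the method changes with the visit: dipstick up to induction, central for Weeks 2 to 5, dipstick again at Week 6. Leaving a component out of an any-positive rule can only lower the proportion positive, so the omission by itself works towards fewer positives at the central visits. The fallback adds a second route: two participants at the same nominal visit can be classified under different rules if one has a dipstick result in place of a central sample.

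A reader of the tables could not see this. SAP 5.7.3 gives rows for opiates/morphine, fentanyl, buprenorphine (limited visits), methadone and overall opioids, and then for non-opioid substances. Oxycodone has no row, so its contribution cannot be separated out.

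What is at stake is the reading of on-treatment opioid use in the sub-study's descriptive tables, in particular comparisons across the changes from dipstick to central testing and back.

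**Working it through.** The plan gives no figure on this point, so there is none to reproduce. The check compares the two rules as written.

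**Inputs.** Let O be the opiates result (central) or the combined opioids/morphine result (dipstick), F fentanyl, M methadone and X oxycodone, each positive or negative with none missing. The paired tests (fentanyl with norfentanyl, opioids with morphine) are taken as already merged. For this comparison O is assumed to have the same value under both methods.

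**Rules.**
- Central (SAP 6.8.1): positive if O or F or M is positive.
- Dipstick (SAP 6.8.2): positive if O or F or M or X is positive.

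**Enumeration.** Four binary results give 2 × 2 × 2 × 2 = 16 patterns.
- If any of O, F or M is positive, both rules return positive: 16 − 2 = 14 patterns, no disagreement.
- If O, F and M are negative and X is negative, both return negative: 1 pattern, no disagreement.
- If O, F and M are negative and X is positive, central returns negative and dipstick returns positive: 1 pattern, disagreement.

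The rules therefore disagree on 1 of 16 patterns, oxycodone alone.

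**With X added to the central rule.** The two expressions become identical, and disagreements fall from 1 of 16 to 0 of 16.

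**If the central opiates test itself reacts to oxycodone.** O is then positive centrally in such a sample. Central returns positive, dipstick returns positive through X, and there is no disagreement.

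**Size.** Let q be the proportion of samples at a central visit that are positive for oxycodone and negative for the other three. The three-test rule reports a positive proportion lower by exactly q than the four-test rule would on the same samples. The documents give no value for q. The number of patterns that disagree says nothing about how often that pattern occurs.

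**The case against.** **Coverage of central opiates.** The strongest objection is that the term may denote a class result that already detects oxycodone. The central rule has no separate morphine input either, although Table 1 lists Morphine on its own, and SAP 5.7.3 uses a joint opiates/morphine label. Both fit a class test. Against that, 6.8.1 speaks of individual results for each opioid drug, and Protocol 8.3.1 applies one list to both methods. The opening sentence of SAP 6.8 is incomplete in the available text, so it cannot settle the matter. A reader might infer that oxycodone-only samples are certainly misclassified; the documents support this only conditionally.

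**Effect on conclusions.** In this SAP the overall UDS result feeds descriptive summaries. It does not enter treatment retention, the non-inferiority test, time to discontinuation or the interim decisions. Both arms share the Week 2 to 6 visit schedule (Protocol Appendix 22.4), so nothing points to a systematic bias between arms. This stands.

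**A step at Week 6.** A reader might infer an artificial rise of some definite size from Week 5 to Week 6. The documents do not support one. The frequency of oxycodone-only samples is not given. The eligibility criteria and Protocol Appendix 22.8 suggest they may be uncommon, without settling on-treatment use. The methods also differ in other ways: the central rule counts norfentanyl and the dipstick rule does not, which could raise central positivity. The net direction is therefore open.

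**The main-study primary endpoint.** A reader might infer that an oxycodone-positive urine would count as abstinent there. That does not follow. This SAP covers the sub-study only, and the main-study UDS derivation is not in these documents. Under Protocol Table 7 a positive TLFB makes the visit positive even when the UDS is negative, and Protocol 8.3.2 lists oxycodone among the drugs the TLFB asks about.

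**Conclusion.** The point holds as a conditional inconsistency. The two written rules use different inputs for a substance that the protocol puts on both panels, and no reason is given. Unless central opiates detects oxycodone, an oxycodone-only sample is opioid-negative at Weeks 2 to 5 and opioid-positive at Screening, Induction Day 1 and Week 6, and the overall opioid summaries in SAP 5.7.3 and 5.7.6 mix the two definitions. If it does detect oxycodone, the classifications agree on this pattern, and what is missing is the definition that shows it.

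The understatement at central visits from this one cause equals the proportion of oxycodone-only samples, which cannot be computed from the documents. The consequence is confined to descriptive sub-study tables; the primary retention result does not depend on it. For the main study the documents support only a check. If the same derivation were used there, only oxycodone use not reported on the TLFB, or use where the TLFB is missing, could be counted as abstinent.

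**What to change.** In SAP 6.8.1, add the central oxycodone result as a fourth component: positive if any of the four is positive, negative if all four are negative, missing otherwise. This is harmless if central opiates already covers oxycodone. Alternatively, state in 6.8.1 that the central opiates result includes oxycodone.

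Leave oxycodone in the dipstick rule in either case. Nothing shows that the dipstick's opioids/morphine result detects oxycodone, so removing it could create the same mismatch in reverse.

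Check that the main-study UDS derivation treats oxycodone in the same way.

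The cost is about one line of SAP text and a small programming change. No new data are needed if the central panel follows Protocol Table 1. One side effect should be accepted knowingly: a central sample with the other three results negative and oxycodone missing would move from negative to missing, as the all-negative requirement in 6.8.2 already implies for the dipstick.

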#### 6.8.2 On-site dipstick UDS

Individual test results for opioids and morphine from the on-site dipstick UDS will be combined into 1 result for opioids/morphine. The algorithm to determine the combined result is as follows:

- "Opioids/morphine Positive" if at least 1 of the individual test results is positive.
- "Opioids/morphine Negative" if both test results are negative; or if 1 is negative and another is missing.
- "Opioids/morphine Missing" if both test results are missing.

The algorithm to determine the on-site dipstick overall UDS opioid result uses 4 test results (1 combined test result for opioids/morphine, and 3 individual test results for oxycodone, methadone, fentanyl) as follows:

- "Opioid Positive" if at least 1 test result is positive.
- "Opioid Negative" if all 4 test results are negative.
- "Opioid Missing" for other scenarios, eg, if all 4 test results are missing; if opioids/morphine is missing and the other 3 test results are negative or missing; if the fentanyl test result is missing and at least one of the other 3 test results is negative.

